3.3 EXPLORATORY ENDPOINTS

The exploratory endpoints of the study are:

- Improvement in disease-related symptoms of fatigue, weight loss, unexplained fevers and night sweats from Baseline
- Minimal Residual Disease (MRD) in subjects with documented CR or CRi
- Health-related QoL of subjects as assessed by the following subject-reported questionnaires:
 - EuroQol-5D (EQ-5D)
 - Functional Assessment of Chronic Illness Therapy-Fatigue (FACIT-F)
- Serum and tissue biomarkers and blood immunophenotype
- Tumor genomic features (eg, DNA sequence variation, DNA copy number variation, and/or RNA expression)
- Germline DNA sequence variations

4 STUDY DESIGN

Study IPI-145-07 is a two-arm, randomized (1:1 ratio), open label, phase 3, superiority trial designed to evaluate the efficacy and safety of duvelisib compared to ofatumumab. Subjects will be stratified by:

1. High-risk cytogenetics (presence vs absence of del[17p])
2. Refractory/early relapse to purine analog based therapy (defined as progression < 12 months after fludarabine/pentostatin: yes vs no)
3. Grade 4 cytopenia(s) (presence vs absence of neutropenia or thrombocytopenia at baseline)

Eligible subjects will be randomized in a 1:1 ratio to one of two treatment arms:

- Arm 1: Duvelisib, 25 mg BID
- Arm 2: Ofatumumab

First dose is to occur within 7 days of randomization after all screening assessments have been completed.

4.1 SCHEDULE OF ADMINISTRATION

Subjects who meet all the eligibility criteria at Screening will return to the clinic on Day 1 to receive their first dose of study drug (either duvelisib or ofatumumab). The first treatment cycle for each treatment arm will be 3 weeks (21±2 days). Subsequent treatment cycles will be 4 weeks (28±4 days).

Arm 1 (Duvelisib): Subjects randomized to duvelisib will receive their first dose of study drug in clinic on Day 1, initiating Cycle 1 of treatment. These subjects will return for a second clinical visit on Day 8±2. Cycle 1 will be 21 days, with all subsequent cycles 28 days in length. Cycle 2 will have clinic visits on Day 1 and on Day 15±2. Each subsequent cycle (Cycle 3-7) and then every odd cycle (Cycle 9 to 19) will have only one clinic visit on Day 1. Subjects will receive duvelisib continuously for 18 cycles or until disease progression or unacceptable toxicity, whichever comes first. After completing approximately 18 cycles of treatment with duvelisib, subjects who, in the judgment of the investigator, may derive benefit from continued treatment may receive additional cycles of duvelisib until disease progression or unacceptable toxicity. However, to receive additional cycles of duvelisib beyond 18 cycles, subjects must have CLL/SLL requiring treatment by Cycle 19 Day 1 (Reference 4.2.1.2). Subjects who receive duvelisib beyond 18 cycles (Cycle 19 Day 1) will maintain clinical visits every odd cycle (Cycle 21, 23, etc) until disease progression, subject withdrawal, or initiation of additional anticancer treatment. After Cycle 18, disease response assessments will continue every 6 cycles for those subjects who have not had disease progression, withdrawn consent, or initiated additional anticancer treatment.

Arm 2 (Ofatumumab): Subjects randomized to ofatumumab will receive IV treatment according to the approved prescribing information.^{10, 11} Subjects will receive 8 weekly IV infusions, starting with an initial dose of ofatumumab of 300 mg followed by seven weekly doses of 2000 mg. Thereafter, subjects will receive 2000 mg ofatumumab once every cycle for four cycles or until disease progression or unacceptable toxicity, whichever comes first.

Administration of ofatumumab will not exceed the 12 doses (within 7 cycles) as described in the prescribing information. After dosing with ofatumumab is complete (ie, through Cycle 7 or ETT), subjects will continue to have clinical assessments every odd cycle (Clinical Assessment Period) through Cycle 19 Day 1 or until disease progression, subject withdrawal, or initiation of additional anticancer treatment. After Cycle 19 Day 1, disease response assessments will continue every 6 cycles until disease progression, subject withdrawal, or initiation of additional anticancer treatment.

If a subject initiates another anticancer therapy following treatment with ofatumumab, then the subject will be discontinued from the Clinical Assessment Period and will be followed for survival as described in [Table 5](#).

Subjects who have documentation of PD confirmed centrally at any time during the study may be eligible to receive the opposite study medication as part of a separate Verastem-sponsored extension protocol (Study IPI-145-12). Additional extension protocol eligibility criteria must also be met.

4.2 DOSE INTERRUPTION/HOLD/MODIFICATION GUIDELINES

4.2.1 Duvelisib Guidelines

Duvelisib treatment will consist of 25 mg administered orally BID continuously for up to 18 cycles. Duvelisib may be continued beyond 18 complete cycles, if the subject meets the criteria for additional treatment at Cycle 19 Day 1 (see [Section 4.2.1.2](#)). Duvelisib dosing may be modified due to benefit or toxicity as described below.

4.2.1.1 *Duvelisib treatment modification guidelines due to duvelisib-related toxicities*

Subjects will be monitored continuously for toxicity while on study treatment. Toxicity will be assessed using the National Cancer Institute Common Terminology Criteria for Adverse Events (NCI CTCAE) Version 4.03. If a subject has an AE at least possibly related to duvelisib, then dose interruptions/holds with possible modifications as described below in [Table 8](#) may be implemented. Deviations from these guidelines may occur based on the clinical judgment of the Investigator with notification to the Medical Monitor/Sponsor. There should be no attempt to make up for missed doses of duvelisib.

Table 8: Dose Interruption/Hold/Modifications for Duvelisib-Related Toxicities

Duvelisib-related Toxicities ^{a, b}	Dose Interruption/Hold/Modification/Recommendation for Duvelisib ^c

Nonhematologic: Grade 2 or higher Pneumonitis/Pneumonia Or Grade 3 or higher other Nonhematologic
	
First occurrence: Withhold until return to ≤Grade 1 or baseline level; re-challenge therapy at original dose level. Second occurrence of the same AE: Withhold until return to ≤Grade 1 or baseline level; re-initiate therapy at one dose level lower from current dose.

Hematologic: Grade 3 or higher febrile neutropenia Or Grade 3 or higher thrombocytopenia with Grade ≥2 hemorrhage.
	
Third occurrence of the same AE: Withhold until return to ≤Grade 1 or baseline level; re-initiate therapy at one dose level lower from current dose. Fourth occurrence of the same AE: Discontinue subject from study drug

Recommendations for implementing duvelisib dose interruptions
 
Immediate hold for Grade 4 or higher nonhematologic toxicity and Grade 3 or higher febrile neutropenia. For all other events, reduce from BID dosing to QD for two days, then hold.
	

- a. Duvelisib-related toxicity = possible, probable, or definite relationship to duvelisib as defined in [Section 8.2.1](#).
- b. Toxicity grades are defined per CTCAE Version 4.03. Note if parameter is not defined by CTCAE, then AE grading criteria ([Section 8.2.1](#)) should be utilized.
- c. Refer to [Table 9](#) for duvelisib dose levels.

Treatment Interruption for Nonhematologic Toxicity

Treatment with duvelisib should be interrupted for the following nonhematologic toxicities:

- Grade 2 or higher pneumonitis/pneumonia, defined as symptomatic and requiring medical intervention, including oral antimicrobials and/or steroids
 - Subjects who develop new pulmonary symptoms (eg, cough, shortness of breath, dyspnea on exertion) or new radiographic findings should have duvelisib held and receive empiric antimicrobial coverage while undergoing evaluation. Corticosteroids for symptomatic treatment of pneumonitis is recommended (and allowed per protocol). Restarting treatment with duvelisib is allowed after complete resolution of symptoms.
- Grade 3 or higher other nonhematologic toxicity including the following:
 - Infections: Subjects who develop infections requiring IV antibiotics/antifungals/anti-virals should have duvelisib held until infection resolves (subject may restart duvelisib when completing a course of oral therapy). Prophylaxis to prevent recurrence/opportunistic infections will not preclude the subject from restarting treatment.
 - Hepatic events: Subjects who develop Grade 3 or higher transaminase (ALT/AST) elevations with or without clinical symptoms should have duvelisib held until return to baseline. Additional work-up to evaluate viral infection/re-activation, exposure to environmental toxins (eg, alcohol/con-meds), or other causes is recommended before restarting treatment with duvelisib.

- **Gastrointestinal:** Subjects who develop Grade 3 or higher nausea, vomiting or diarrhea despite optimal treatment should have duvelisib held until resolution of symptoms. Evaluation of concomitant medications, gastrointestinal infections or inflammatory bowel (via endoscopy and biopsy) should be considered with persistent diarrhea or recurrence with restarting duvelisib. Corticosteroids (budesonide) with taper are allowed if colitis is suspected/cannot be ruled out.
- **Skin rash:** Subjects who develop Grade 3 or higher skin rashes should have duvelisib held until resolution of symptoms. In the setting of new Grade 1-2 skin rash early intervention is recommended to ameliorate risk of worsening symptoms. Evaluation of concomitant medications, environmental exposure, infections or other contributing factors is recommended.
- **Cardiac:** Subjects who develop Grade 3 or higher cardiac events should have duvelisib held until resolution of symptoms. This includes \geq Grade 3 (≥ 500 ms) QT interval corrected with Fridericia's method (QTcF) prolongation. A \geq Grade 3 QTcF prolongation requires triplicate ECGs with the average measurement used and the use of Fridericia's correction method (QTcF). For subjects with a right or left BBB, a Grade 3 QTc prolongation is defined as an increase in QTcF of >100 ms from the pre-dose ECG to any post dose ECG as the QRS interval is prolonged at Baseline (by approximately 40 ms) in subjects with a BBB

Subjects requiring treatment interruption should be re-evaluated at least weekly until the toxicity improves to \leq Grade 1 or returns to Baseline level. Duvelisib dose will be restarted at doses described in [Table 9](#).

Treatment Interruption for Hematologic Toxicity

Worsening or transient Grade 3 or higher neutropenia, anemia, and/or thrombocytopenia caused by the subject's existing disease (CLL or SLL) or by duvelisib are to be expected. Blood counts should be monitored as prescribed in the protocol with the frequency increased as clinically indicated in the setting of new or worsening Grade 3 or higher cytopenias. Duvelisib dosing may be interrupted at any time, at the discretion of the treating physician.

Treatment with duvelisib should be interrupted for the following symptomatic hematologic toxicities:

- Grade 3 or higher febrile neutropenia
- Grade 3 or higher thrombocytopenia associated with Grade 2 or higher haemorrhage

The subject should be re-evaluated at least weekly until the toxicity improves to \leq Grade 1 or returns to Baseline.

Duvelisib may be withheld up to 42 days for toxicity. Doses withheld for > 42 days due to treatment-related toxicity will result in permanent discontinuation from treatment. Any subject who requires a dose < 5 mg BID due to treatment-related toxicities will be permanently discontinued from treatment. Dose levels are shown in [Table 9](#).

Table 9: Dosing Levels Duvelisib

Dose Level	Dose (mg)
1	25 BID
-1	15 BID
-2	10 BID
-3	5 BID

Subjects who have a dose reduction due to a toxicity may be eligible for a dose increase back to the dose level prior to the reduction (ie, the starting dose or dose of previous reduction if subject was dose reduced more than one level) if the following criteria are met:

1. Subject has tolerated the lower treatment dose for >1 treatment cycle
2. Subject has recovered to baseline levels from the toxicity which caused the dose reduction

4.2.1.2 Duvelisib treatment modification guidelines due to benefit/maximal benefit.

Treatment discontinuation due to benefit after < 18 complete cycles of duvelisib therapy:

Prior to completion of 18 cycles of duvelisib therapy, discontinuation of duvelisib may be considered, after discussion with the medical monitor, should a CLL subject demonstrate a CR/CRi per IWCLL 2008 criteria or an SLL subject demonstrate a CR per IWG 2007 criteria (see Section 6.3.9 for definitions). The timing of duvelisib treatment discontinuation relative to the duration of a CR should be considered as follows:

- < 12 months of duvelisib therapy: duration of CR/CRi > 6 months before discontinuation
- \geq 12 months of duvelisib therapy: duration of CR/CRi > 3 months before discontinuation

Disease response assessments by CT scan will continue every 6 cycles until disease progression (see Table 5).

Treatment discontinuation after 18 or more complete cycles of duvelisib therapy:

After completion of 18 cycles (beginning on Day 1 Cycle 19) of duvelisib therapy, discontinuation of duvelisib may be considered if a subject demonstrates the following responses (per modified IWCLL criteria/IWG criteria or as otherwise indicated [see Section 6.3.9]) of > 3 months duration:

- CR or CRi
- Partial response (that includes all target lesions \leq 1.5 cm in diameter) but with a peripheral blood absolute lymphocyte count (ALC) \geq 4,000/ μ L (Rai Stage 0)

- Persistent lymphadenopathy > 50% of baseline (with at least 1 target lesion \geq 1.5 cm in diameter) and persistent lymphocytosis \geq 4,000/ μ L (and > 50% of baseline)

Disease response assessments by CT scan will continue every 6 cycles until disease progression (see [Table 5](#)).

Treatment continuation after 18 or more complete cycles of duvelisib therapy:

Duvelisib therapy may continue if there is potential benefit to the subject based on the following disease response assessments (per IWCLL criteria /IWG criteria or as otherwise indicated [see [Section 6.3.9](#)]) at the end of 18 cycles (Day 1 Cycle 19) of duvelisib therapy:

- CR or CRi < 3 months duration
- PR with or without lymphocytosis
- SD

Disease response assessments by CT scan will continue every 6 cycles while the subject remains on duvelisib treatment (see [Table 5](#)).

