- c. Additional (unscheduled) assessments should be done as clinically indicated. Blood samples should be drawn and results reviewed within 72 hours of the designated clinic visit.
- d. Screening evaluations performed within 7 days of Cycle 1 Day 1 can be used and assessments do not need to be repeated at Cycle 1 Day 1 (predose)
- e. Drawn only on Day 1 of Cycles 3, 5, 7, 11, 15, 19, and ETT. Blood for immunophenotyping, serum for biomarkers, and blood for biomarkers do not need to be collected beyond the ETT visit or treatment discontinuation.
- f. May be either urine or serum, and performed every odd cycle while on treatment.
- g. To be sent to the central laboratory.
- h. Sample may be drawn at screening or Cycle 1 Day 1 (predose). Collection at Cycle 1 Day 1 is preferred. If drawn at screening, a sample is not needed at Cycle 1 Day 1.
- i. This sample will be analyzed centrally and is separate from the documentation of prior del(17p) analysis required for eligibility and stratification.
- j. Additional blood for immunophenotyping/biomarker serum samples may be requested from any subject receiving duvelisib at qualified sites (when feasible) at the time of a drug interruption/hold due to an AE, or for any usual safety event or efficacy event.
- k. Samples on Cycle 1 Day 1 should be drawn predose.
- l. Pharmacogenomics sample (buccal swab) is optional.
- m. QoL assessments to be captured at on Day 1 of Cycles 3, 5, 7, 11, 15, and 19 until disease progression, subject withdrawal, or initiation of additional anticancer therapy, and when possible, at the ETT (if >1 month from last administered questionnaire).
- n. Requests for archival tissue (pretreatment sample) should be initiated at Cycle 1 Day 1. In the event a request is placed but no archival tissue can be located, this sample type is not required.
- o. Subjects who discontinue treatment from duvelisib prior to Cycle 19 Day 1 for reasons other than PD, will maintain the clinical visit schedule through Cycle 19 Day 1 until disease progression, subject withdrawal, or initiation of additional anticancer therapy.
- p. Subjects who, in the judgment of the investigator, may derive benefit from continued treatment, may receive additional cycles of duvelisib beyond Cycle 19 Day 1 until disease progression or unacceptable toxicity. .

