- q. The Early Treatment Termination (ETT) Visit should occur for any subject who discontinues duvelisib treatment prior to Cycle 19 Day 1. The ETT assessments need not be performed if the subject has had a previous assessment within the previous 2 weeks or previous 30 days for Disease Response Assessments [see [Table 5](#)] and the QoL assessment.

Table 3: Pharmacokinetic Assessments for Subjects Receiving Duvelisib Only ^a

	Cycle 2 ^d			Cycle 3	Cycle 7
	Day 1±2			Day 1±2	Day 1±2
Time (h) relative to duvelisib administration	Predose	0.5-2h	3-5h	Anytime	Anytime
Pharmacokinetic blood sample collection ^{b, c}	X	X	X	X	X

- a. See [Section 6.3.7](#) for additional information on pharmacokinetic (PK) assessments.
- b. The date and time of the PK samples will be recorded, along with the date and time of the previous two doses of duvelisib.
- c. Additional PK samples may be requested from any subject receiving duvelisib at qualified sites (when feasible) at the time of a drug interruption/hold due to an AE, or for any usual safety event or efficacy event.
- d. The morning dose of duvelisib will be administered in the clinic on Cycle 2 Day 1.

Table 4: Schedule of Assessments for Subjects Receiving Ofatumumab ^a

	Cycle 1 (21±2 days) ^o			Cycle 2 (28±4 days) ^o				Cycle 3-7 (28±4 days) ^o	Early Treatment Termination (ETT) ⁿ from Ofa ≤ 7 d from last dose	Safety Follow-up Visit 30+7d from last dose	Clinical Assessment Period ^o C9-C19 (28±4 days) Day 1±4
	Ofa 300 mg D1	Ofa 2000 mg D8±2	Ofa 2000 mg D15±2	Ofa 2000 mg D1±2	Ofa 2000 mg D8±2	Ofa 2000 mg D15±2	Ofa 2000 mg D22±2	Ofa 2000 mg D1±4			
Concomitant Meds & Procedures	X	X	X	X	X	X	X	X	X	X	X
AE/SAE assessment ^b	X	X	X	X	X	X	X	X	X	X	
Focused physical exam	X			X				X	X		X
Blood chemistry ^c	X ^d	X		X		X		X	X		X
Hematology ^c	X ^d	X		X		X		X	X		X
Coagulation tests ^c	X ^d										
Serum Immunoglobulins	X							X ^e	X ^e		X ^e
βhCG pregnancy test ^{c,f}								X	X		
Blood for Cytogenetics /FISH analysis ^g	X ^{h,i}										
Blood for IGHV mutation analysis ^g	X ^h										
Blood for Immunophenotyping ^g	X ^j							X ^e	X ^e		X ^e
Serum for biomarkers ^g	X ^j			X				X ^e	X ^e		X ^e
Blood for biomarkers ^g	X ^j			X				X ^e	X ^e		X ^e
Pharmacogenomics ^g	X ^k										
EQ-5D & FACIT-F	X ^d							X ^l	X ^l		X ^l
ECOG performance status	X ^d	See Table 5: Disease Response Assessments									
Response assessments		See Table 5: Disease Response Assessments									
Archival tumor tissue	X ^m										

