- n. The Early Treatment Termination (ETT) Visit should occur for any subject who discontinues ofatumumab treatment prior to Cycle 7 Day 1. ETT assessments need not be performed for those assessments performed within the previous 2 weeks (previous 30 days for Disease Response Assessments [see [Table 5](#)] and the QoL assessment).
- o. The clinical visit schedule should be maintained until Cycle 9 for subjects who discontinue study treatment prior to Cycle 9 for reasons other than PD. The clinical assessment period then begins at Cycle 9, with visits occurring every other month until disease progression, subject withdrawal, or initiation of additional anticancer therapy; no additional study drug (ofatumumab) will be administered.

Table 5: Disease Response & Follow-up Assessments for All Subjects

Assessments ^d	Screening (baseline)	Cycle 3 Day 1	Cycles 5, 7, 11, 15, & 19 Day 1	Early Termination from Study Treatment (ETT) ^a ≤7 days of last dose	Disease Follow-up ^b Every 6 months (±4 weeks)	Survival Follow-up ^c Every 6 months (± 4 weeks)
CT scans of chest, abdomen and pelvis ^e	X	X	X	X	X	
Bone marrow biopsy and/or bone marrow aspiration ^f	X	X	X	X	X	
Complete blood count (CBC) and differential count ^g	X	X	X	X	X ⁱ	
Blood sample for assessment for minimum residual disease (MRD) ^h		X	X	X	X	
Focused physical examination ^g , disease related constitutional symptoms assessment, and ECOG performance status	X	X	X	X	X	
Survival						X

- a. ETT Disease Response Assessment is not necessary if a Disease Response Assessment was performed within the previous 30 days. In the absence of disease progression or initiation of subsequent anticancer therapy, all subjects with ETT prior to Cycle 19 Day 1 will maintain the disease response assessment schedule (Cycles 5, 7, 11, 15, & 19)
- b. All subjects with no disease progression by Cycle 19 Day 1 will continue Disease Response Assessments (Section 6.5.3.1) every 6 months until disease progression, subject withdrawal, or initiation of additional anticancer therapy. The first disease follow-up assessment after Cycle 19 Day 1 should occur approximately 6 months after last disease assessment.
- c. All subjects will have Survival Follow-up for up to 6 years after randomization or until death. This assessment can be conducted by telephone interview. Information on initiation of other anticancer therapy (including start date, therapy type, and response on treatment) will also be collected.

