4.3 TREATMENT DISCONTINUATION

A subject should be withdrawn from the study treatment if, in the opinion of the investigator, it is medically necessary, or if it is the wish of the subject.

Subjects will be withdrawn from treatment in case of any of the following reasons:

- An adverse event that requires permanent discontinuation of duvelisib or ofatumumab
- Protocol-specified disease progression
- Subject death
- Subject lost to follow-up
- Noncompliance to protocol
- Investigator decision (including for benefit as described in [Section 4.2.1.2](#))
- Subject becomes pregnant
- Termination of the study by sponsor
- Voluntary withdrawal by subject
- Subject requires additional anticancer therapy

Adverse events leading to the discontinuation of a subject will be followed until resolution, resolution to baseline or until the event is considered stable or chronic.

If a subject does not complete dosing through Cycle 19 Day 1 (duvelisib) or through Cycle 7 (ofatumumab), then he/she should attend an Early Treatment Termination (ETT) Visit within 7 days of last dose or the decision leading to treatment discontinuation (see [Section 6.4](#)). Assessments collected within 14 days of the ETT (within 30 days for Disease Response Assessment and QoLs) Visit do not need to be repeated at the ETT Visit. Following last dose, either due to ETT or completion of dosing, all subjects will complete a 30-day safety follow-up visit (see [Section 6.5.1](#)). Scans will be performed at the ETT if a previous scan has not been performed within 30 days of the ETT visit. All subjects who discontinue treatment will be followed for survival (see [Section 6.5.3.2](#)).

Subjects who discontinue study treatment for reasons other than PD, and have not withdrawn consent from overall study participation should enter the Clinical Assessment Period ([Section 6.5.2](#)) and continue Disease Response Assessments ([Section 6.5.3.1](#)) as applicable.

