6.3.9.1 CT Scans

CT scans (contrast-enhanced preferred) of the chest, abdomen, and pelvis are required for all subjects to document measureable disease at baseline and will be performed as outlined in [Table 5](#). Other scans may be performed (eg, head CT) if clinically indicated or if the area is a site of known disease. MRI may be substituted if clinically indicated, but the modality chosen to evaluate each individual subject should be the same throughout the duration of the study.

If the subject is discontinued early from study treatment (eg, before Day 1 Cycle 7 of ofatumumab study treatment or before Day 1 Cycle 19 of duvelisib study treatment) and a previous assessment has not been performed within 30 days, CT scans will be also performed at the ETT and the subject will continue to undergo assessments as outlined in Disease Follow-up in [Table 5](#).

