6.5.3 Follow-up

6.5.3.1 Disease Follow-up

Subjects who discontinue treatment with duvelisib or ofatumumab early (ie, ETT) due to reasons other than PD will continue to undergo disease response assessments up until Cycle 19 Day 1 (ie, Cycles 5, 7, 11, 15 and 19) or until disease progression, subject withdrawal, or initiation of additional anticancer therapy. After Cycle 19 Day 1, all subjects without progressive disease will enter Disease Follow-up. CBC and differential count will be performed approximately 3 months after the last assessment, and every 3 months thereafter until disease progression, subject withdrawal, or initiation of additional anticancer therapy. All other disease assessments should occur approximately 6 months after the Cycle 19 Day 1 Disease Response Assessment, and every 6 months thereafter until disease progression, subject withdrawal, or initiation of additional anticancer therapy. The following assessments should be performed as outlined in [Table 5](#).

Every 3 months

- CBC and differential count

Every 6 months

- CT scans of chest, abdomen and pelvis
- Bone marrow biopsy and/or bone marrow aspiration (when clinically indicated)
- Blood sample for assessment for minimum residual disease (MRD) in subjects with documented CR or CRi
- Focused physical examination, ECOG performance status, and disease-related constitutional symptoms

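### Protocol 4.2.1.2 sets a sparser CT schedule after an early duvelisib stop for complete response than Table 5 allows (minor)

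*Protocol*

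**What the plan says.** Most of the protocol gives one schedule for a subject who stops treatment before Cycle 19 Day 1 without progression.

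- Table 2, footnote q: "The Early Treatment Termination (ETT) Visit should occur for any subject who discontinues duvelisib treatment prior to Cycle 19 Day 1". A stop for benefit is not exempt.
- Table 5, footnote a: "all subjects with ETT prior to Cycle 19 Day 1 will maintain the disease response assessment schedule (Cycles 5, 7, 11, 15, & 19".
- Section 6.5.3.1 repeats this: such subjects "will continue to undergo disease response assessments up until Cycle 19 Day 1 (ie, Cycles 5, 7, 11, 15 and 19".
- Table 2, footnote o: subjects who stop duvelisib early "for reasons other than PD, will maintain the clinical visit schedule through Cycle 19 Day 1".
- Section 4.3: those who stop for reasons other than PD and "have not withdrawn consent from overall study participation should enter the Clinical Assessment Period".
- Table 5, footnote b starts the 6-monthly follow-up only at Cycle 19: "All subjects with no disease progression by Cycle 19 Day 1 will continue Disease Response Assessments". Footnote e describes the CT frequency in the table as the least that participation requires.

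Two passages differ. Section 4.2.1.2, in the paragraph on stopping for CR/CRi before 18 complete cycles, says: "Disease response assessments by CT scan will continue every 6 cycles until disease progression (see Table 5". Section 6.3.9.1 says of early stoppers in either arm that "CT scans will be also performed at the ETT and the subject will continue to undergo assessments as outlined in Disease Follow-up in" Table 5, where the column of that name is 6-monthly.

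The PFS censoring table (protocol Table 13, SAP V4.0 Appendix A) censors a progression or death that follows a long gap. Its example of a long gap is two or more scheduled assessments missed in a row. Appendix B carries the same rule for EFS. None of the three names the schedule. SAP 5.1 leaves the detailed algorithm to the ADaM specifications, which are not among the documents.

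**The concern.** PFS by central review depends on when scans are taken. The benefit stop exists only for duvelisib. A longer scan interval attached to it is therefore a difference in endpoint ascertainment between the arms, in an open-label trial whose other provisions keep both arms on one calendar. Later detection lengthens PFS in that arm.

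The gap rule adds a second route. A site that follows 4.2.1.2 faithfully could leave two Table 5 assessments undone. Whether a progression found at the next scan is an event or a censored time would then depend on which of the two schedules the programmer counts against. Both routes would act in the duvelisib arm only, and in its favour.

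**Working it through.** The plan states no figure to reproduce here. The check compares schedules and counts days.

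**Inputs.** Cycle 1 lasts 21 days and later cycles 28 (protocol 4.1). Counting Cycle 1 Day 1 as day 0, Day 1 of cycle c falls on day 21 + 28 × (c − 2). This gives Cycle 3 = 49, 5 = 105, 7 = 161, 9 = 217, 11 = 273, 13 = 329, 15 = 385, 17 = 441 and 19 = 497. Six months are taken as 183 days. Visit windows and the lag from randomization to first dose are ignored.

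**Intervals.** Table 5 from Cycle 7: 273 − 161 = 385 − 273 = 497 − 385 = 112 days. Section 4.2.1.2: 6 × 28 = 168 days. If progression is equally likely at any time within an interval, the mean wait to the next scan is half the interval: 168/2 = 84 against 112/2 = 56, so 28 days later on average. Single cases can go either way. After a stop at Cycle 11, a progression on day 400 is found on day 441 under 4.2.1.2 and on day 497 under Table 5.

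**Earliest benefit stop.** Under 12 months of therapy, the CR/CRi must have lasted more than 6 months. The first response assessment is Cycle 3, so 49 + 183 = 232 and the earliest stop is day 233. The clinic visits left before Cycle 19 are Cycles 11, 13, 15 and 17.

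**Assessments skipped.** The next scan is taken as the last scan + 168 days, assuming the six cycles run from the last scan. Section 4.2.1.2 does not say where they start. At Cycles 13 and 17 the previous scheduled scan is 56 days old, and on day 340 it is 340 − 273 = 67 days old. Both exceed the 30-day waiver, so an ETT scan is due.

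| Stop and last scan | Day | Next scan | Table 5 assessments in between |
|---|---|---|---|
| Cycle 11 | 273 | 441 | Cycle 15 |
| Cycle 13 | 329 | 497 (Cycle 19 itself) | Cycle 15 |
| Cycle 15 | 385 | 553 | Cycle 19 |
| Cycle 17 | 441 | 609 | Cycle 19 |
| Between visits | 340 | 508 | Cycles 15 and 19 |

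In the last row, a progression found on day 508 is censored at day 340 if misses are counted on Table 5, and is an event on day 508 if they are counted on 4.2.1.2. If the six cycles run instead from the last Table 5 visit (Cycle 11, day 273), the next scan is day 441, only Cycle 15 is skipped, and the progression stays an event.

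**Reach.** The documents give no rate of stopping for benefit. As an assumption, apply the phase 1 CR rates in protocol Table 7: 150 × 1/30 = 5.0 duvelisib subjects at 25 mg BID or less (exact 95% limits 0.1 to 25.8), or 150 × 1/52 = 2.9 over all doses (0.1 to 15.4). CRi is not listed there. Only those who hold the response long enough and then stop follow this route, and only off-visit stops can skip two assessments.

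**The case against.** The strongest reply is that the protocol already settles the schedule. Section 6.3.9 ties response and progression assessment to Table 5. Footnote a covers all early stoppers, footnote e makes the table's CT frequency a minimum, and 4.2.1.2 itself points to Table 5. On that view a site scanning every 168 days deviates from the protocol and is not following a second valid schedule. Stops would normally be decided at a clinic visit, where only one assessment is skipped. Clinic visits with blood counts and examination continue to Cycle 19, and SAP 6.7 brings unscheduled assessments into the endpoint, so the central review may reach a disease status in between.

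Most of this stands, and it keeps the point small. It does not remove the contradiction. Section 4.2.1.2 states an interval that the table it cites does not contain before Cycle 19, and a site following that sentence would fall below the minimum.

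A reader might infer three stronger things that the documents do not support.

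- That all early stoppers in both arms move to 6-monthly scans under 6.3.9.1. Footnotes a and b resolve that pointer, and 6.5.3.1, which sets out the cycle schedule, is itself headed Disease Follow-up. It is a loose cross-reference.
- That the gap rule has no schedule behind it. Table 5 is its natural reference, and the ADaM specifications may define a miss. The rule needs a clarifying sentence, but that alone would be missing detail and not an error.
- That a material share of PFS events would be censored. This needs a stop between visits, a clock starting at the ETT scan, misses counted on Table 5, and no disease status from central review in between.

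**Conclusion.** The contradiction in 4.2.1.2 is real, and its severity is minor. Followed as written, it gives some duvelisib subjects, and no ofatumumab subjects, 168-day instead of 112-day CT intervals before Cycle 19. Gap-rule censoring of a documented progression is possible, but only under the conditions just listed.

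The group is probably a handful of subjects, on the assumption that the phase 1 CR rate carries over. The effect on the hazard ratio cannot be computed, because the documents do not say how many subjects will stop early without progression. The stated power of approximately 93% with 185 events is not affected by this point. The same 6-cycle sentence for stops after 18 or more cycles is not at issue: 168 days is close to the 6-monthly follow-up that applies from Cycle 19.

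**What to change.** 1. In protocol 4.2.1.2, reconcile the scan sentence for stops before 18 cycles with Table 5 footnote a and 6.5.3.1, so that one disease assessment schedule after an early stop applies to both arms.
2. In protocol 6.3.9.1, correct the cross-reference to match (editorial).
3. As a consequence, state in protocol Table 13 and SAP Appendices A and B that missed scheduled assessments are counted against that Table 5 schedule.

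The cost is a wording change in two protocol passages and one sentence in each of the three censoring tables. It adds no procedure, and no scan beyond those Table 5 already requires.
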